## 6.8 Behavioral Measures

At enrollment and during follow up visits as noted in Appendix 1a, participants will complete a brief ACASI questionnaire at a private computer terminal located at the study site.

Participants will be queried on the contextual factors and experiences which have shown to have an impact on product use and HIV risk. Items from the following domains will be included in the ACASI interview or eCRF at some or all visits as appropriate:

- Sociodemographic characteristics
  - Gender identity
  - Race/Ethnicity
  - Housing situation
  - Employment status
  - Income, including sex work engagement
- Partnership characteristics and partner's HIV status
- Sexual behaviors
- HIV risk perception
- Barrier and facilitators to PrEP use
- Alcohol and drug use
- Intimate Partner Violence
- Interest in emerging HIV prevention interventions
- Hormonal therapy use and adherence
- Non-prescription hormone and/or soft-tissue filler use including sites of soft-tissue fillers/implants
- Anatomy inventory
- Social, legal and medical gender affirmation
- Access to gender and primary care services
- Beliefs about drug-drug interactions between hormones and PrEP

The acceptability of the intervention and standard of care will also be assessed:

- Co-location of hormonal therapy and PrEP services
- Peer navigation using SBCM
- Referral link to GAHT (as appropriate)

Site Community Advisory Boards (CAB) will assist in developing and piloting this questionnaire.

## 6.9 Interim Contacts and Visits

Interim contacts and visits may take place between regularly scheduled visits. These contacts/visits may be done at participant request (e.g., to receive further counseling or clarify

any questions) or as deemed necessary by the investigator or designee at any time during the study (e.g., to follow-up on an adverse event). Procedures to be performed during these contacts/visits will be based on the reason for it. All interim contacts and visits will be documented in participants' study records and on eCRFs, if applicable.

## **7.0 SAFETY MONITORING AND ADVERSE EVENT REPORTING**

### **7.1 Adverse Event Definition and Reporting**

An adverse event (AE) is defined as any untoward medical occurrence in a clinical research participant administered an investigational product and which does not necessarily have a causal relationship with an investigational product. As such, an AE can be an unfavorable or unintended sign (including an abnormal laboratory finding, for example), symptom or disease temporally associated with the use of an investigational product, whether or not considered related to the product.

With appropriate permission of the participant, whenever possible, records from all non-study medical providers related to AEs will be obtained and required data elements will be recorded on study eCRFs. All participants reporting an AE will be followed clinically, until the AE resolves (returns to baseline) or stabilizes.

Study site staff will document in source documents all AEs independently of grading or relationship to study products (e.g. PrEP or hormonal therapy). AEs that will be reported on an eCRF are:

- Grade 3 or higher AEs regardless of relatedness to study products
- Any AE that leads to a study product hold (temporary or permanent) or change in regimen regardless of severity and presumed relationship to study products.
- All Serious Adverse Event (SAE)/ Expedited Adverse Event (EAE)

See Section 7.5 for information on grading of severity of events.

Relatedness is an assessment made by a study clinician of whether or not the event is related to study products. The relationship of all AE to study products (as defined in Section 5.1) will be assessed as specified in Version 2.0, January 2010 of the DAIDS Expedited Adverse Event (EAE) Reporting Manual.

### **7.2 Expedited Adverse Event (EAE) Reporting**

Requirements, definitions, and methods for expedited reporting of adverse events are outlined in Version 2.0 of the DAIDS EAE Manual, which is available on the DAIDS Regulatory Support Center (RSC) website at <https://rsc.niaid.nih.gov/clinical-research-sites/manual-expedited-reporting-adverse-events-daims>.

### **7.3 Reporting to DAIDS**

The DAIDS Adverse Event Reporting System (DAERS), an internet-based reporting system, must be used for EAE reporting to DAIDS. In the event of system outages or technical

difficulties, EAEs may be submitted via the DAIDS EAE form. This form is available on the DAIDS RSC website at <https://rsc.niaid.nih.gov/clinical-research-sites/paper-eae-reporting>. For questions about DAERS, please contact NIAID CRMS Support at [[contact]](mailto:[contact]). Please note that site queries may also be sent from within the DAERS application itself.

For questions about expedited reporting, please contact the DAIDS RSC Safety Office at [[contact]](mailto:[contact]).

#### **7.4 Reporting Category for this Study**

The Serious Adverse Event (SAE) Reporting Category, as defined in Version 2.0 of the DAIDS EAE manual, will be used for this study (the definition of an SAE is also included in the manual).

These reporting requirements are required for each study participant from enrollment (defined as the act of randomization) until their follow-up in the study ends. After this time, sites must report to DAIDS serious, unexpected, clinical suspected adverse drug reactions, as defined in Version 2.0 of the DAIDS EAE manual, if the study site becomes aware of the event on a passive basis, i.e., from publicly available information.

In addition to submitting EAE information to the DAIDS Safety Office via DAERS, the site investigator may be required to submit AE and EAE information to local regulatory agencies or other local authorities.

Site staff will report information regarding AEs to their IRB in accordance with all applicable regulations and local IRB requirements.

#### **7.5 Grading Severity of Events**

The Division of AIDS Table for Grading the Severity of Adult and Pediatric Adverse Events, Corrected Version 2.1, July 2017, will be used for determining and reporting the severity of adverse events. The DAIDS grading table is available on the DAIDS RSC website at <https://rsc.niaid.nih.gov/clinical-research-sites/daids-adverse-event-grading-tables>.

#### **7.6 Social Impact Reporting**

It is possible that participants' involvement in the study could become known to others, and that a social impact may result (i.e., because participants could be perceived as being HIV-infected or at risk or "high risk" for HIV infection). For example, participants could be treated unfairly, or could have problems being accepted by their families and/or communities. A social impact that is reported by the participant and judged by the IoR/designee to be serious or unexpected will be reported to the responsible site's IRBs at least annually, or according to their individual requirements. Social impacts will be collected and reported on applicable eCRF(s) during regular visits. In the event that a participant reports a social impact, every effort will be made by study staff to provide appropriate care and counseling to the participant as necessary, and/or referral to appropriate resources for the safety of the participant. Each site will provide such care and counseling in accordance with standardized guidance in the SSP Manual. While maintaining participant confidentiality, study sites may engage their CAB in exploring the social context surrounding instances of social impacts, to minimize the potential occurrence of such an impact.

## **8.0 STATISTICAL CONSIDERATIONS**

### **8.1 Review of Study Design**

This is a multi-site, open-label study with each participant randomized 1:1 to an Immediate Intervention Arm vs. Deferred Intervention Arm. The study is designed to evaluate whether an intervention that integrates HIV prevention services co-located with GAHT and supported by PHN using SBCM, demonstrates greater engagement in the HIV prevention strategies for HIV-uninfected TGW compared to SOC (i.e., referral for GAHT and case management).

### **8.2 Endpoints**

#### **8.2.1 Primary Endpoints**

Consistent with the primary study objective to assess acceptability and feasibility of delivering integrated HIV prevention services co-located with gender-affirming hormone therapy (GAHT) and PHN using SBCM for TGW, the following endpoints will be assessed:

- Number of participants accepting co-located GAHT services at baseline and subsequent quarterly study visits.
- Number of participants who report desire for co-located services at the end of the study.
- Number of participants retained at Weeks 26, 52 and 78 per study arm.
- Number and content (tracking a participant vs. engagement with a participant) of Peer Health Navigator contacts (text message, email, phone, in-person).

Consistent with the primary study objectives to assess PrEP adherence and persistence for HIV-uninfected TGW in the Immediate Intervention Arm vs HIV-uninfected TGW in the Deferred Intervention Arm, the following congruent endpoints will be assessed:

- Time to PrEP initiation as documented in study eCRFs.
- TFV-DP and FTC-TP levels in DBS measured at quarterly follow up visits after PrEP initiation.
- Drug not dispensed among those who initiate PrEP.
- Self-reported adherence to daily PrEP.
- Time to first PrEP discontinuation

#### **8.2.2 Secondary Endpoints**

Consistent with the secondary study objectives of determining annual incidence of HIV infection, the following endpoint will be assessed:

- Number of documented incident HIV infections during follow-up.

Consistent with the secondary study objectives of determining baseline prevalence and annual incidence of STIs (gonorrhea [GC], chlamydia [CT], and syphilis) and to examine changes in STI incidence over time by study arm, the following endpoint(s) will be assessed:

- Prevalence of STI infection (GC, CT, syphilis) at baseline.
- Incidence of STI infection (GC, CT, syphilis) during follow-up.

Consistent with the secondary study objective of examining changes in sexual risk-taking behavior (e.g., number of serodiscordant or HIV-unknown serostatus sexual partners; number of condomless anal/vaginal sex episodes with these partners):

- Sexual risk-taking behaviors (e.g., number of serodiscordant or HIV-unknown serostatus sexual partners; number of condomless anal/vaginal sex episodes with these partners) measured by ACASI assessments at enrollment and quarterly through Week 78.

Consistent with the secondary study objective of evaluating the cohort's suitability for future PrEP intervention studies (e.g., prevalence of renal insufficiency, hepatitis B virus (HBV) infection, hepatitis C virus (HCV) infection, etc.), the following endpoint(s) will be assessed:

- Baseline laboratory data on all participants.

Consistent with the secondary study objective to identify demographic, behavioral, socioeconomic, and psychosocial factors related to: (1) PrEP uptake and PrEP adherence over time, (2) PrEP persistence, and (3) interest in future HIV research, including research involving injectable and implantable agents for PrEP among HIV-uninfected TGW:

- Individual-level qualitative interview data on a subset of participants addressing core reasons for initiating, discontinuing and/or refusing PrEP.
- ACASI data addressing core reasons for initiating, discontinuing and/or refusing PrEP.
- Interest in future HIV research, collected at Enrollment and Weeks 26, 52, and 78.
- Additional demographic, behavioral, socioeconomic, and psychosocial characteristics collected at Enrollment and quarterly through Week 78.

Consistent with the secondary study objective to assess use of medically-prescribed and non-prescription gender-affirming interventions, including exogenous hormones, soft tissue fillers/silicone, and feminizing surgeries (e.g., breast augmentation, vaginoplasty/labiaplasty, orchectomy, etc.), the following endpoint(s) will be assessed:

- ACASI and/or interviewer-administered questionnaires inquiring frequency and type of intervention in the past three months at enrollment and quarterly follow up visits.

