### **2.2 Secondary Objectives**

The secondary objectives of this study are:

- To determine annual incidence of HIV infection among study participants.
- To determine baseline prevalence and annual incidence of STIs (*Neisseria gonorrhoeae* [GC], *Chlamydia trachomatis* [CT], and *Treponema pallidum* (syphilis)) and to examine changes in STI incidence over time by study arm.

- To examine changes in sexual risk-taking behavior (e.g., number of serodiscordant or HIV-unknown serostatus sexual partners; number of condomless anal/vaginal sex episodes with these partners).
- To obtain baseline laboratory data to evaluate the cohort's suitability for future PrEP intervention studies (e.g., prevalence of renal insufficiency, hepatitis B virus (HBV) infection, hepatitis C virus (HCV) infection, etc.).
- To identify demographic, behavioral, socioeconomic, and psychosocial factors related to: (1) PrEP uptake and PrEP adherence over time, (2) PrEP persistence, and (3) interest in future HIV research, including research involving injectable and implantable agents for PrEP among HIV-uninfected TGW.
- To assess use of medically-prescribed and non-prescription gender-affirming interventions, including exogenous hormones, soft tissue fillers/silicone, and feminizing surgeries (e.g., breast augmentation, vaginoplasty/labiaplasty, orchectomy, etc.).

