### **4.1 Inclusion Criteria**

TGW (assigned male at birth, trans-feminine spectrum – as defined in the SSP Manual – by self-report) who meet all of the following criteria are eligible for inclusion in this study.

1. Eighteen years or older at the time of screening.
2. Willing and able to provide informed consent for the study.
3. Interest in PrEP – as defined in the SSP Manual.

4. Non-reactive HIV test results at Screening and Enrollment.
5. Available to return for all study visits and within site catchment area, as defined per site's Standard Operating Procedures (SOP).
6. At risk for sexually acquiring HIV infection based on self-report of at least one of the following:
  - a) Any anal or vaginal sex with one or more serodiscordant or HIV-unknown serostatus sexual partners in the previous 3 months, regardless of condom use.
  - b) Anal or vaginal sex in exchange for money, food, shelter, or other goods or favors in the previous 3 months.
  - c) History of STI(s) in the past 6 months.
7. Willing to undergo all required study procedures.
8. General good health, as evidenced by the following laboratory values:
  - a) Calculated creatinine clearance  $\geq$  60 mL/minute using the Cockcroft-Gault equation.
  - b) Alanine aminotransferase (ALT) and aspartate aminotransferase (AST)  $<$  2.5 times the upper limit of normal (ULN.)
  - c) HBV surface antigen (HBsAg) negative.

*Note: Otherwise eligible participants with laboratory results outside the above-mentioned values, with the exception of those with reactive HIV test, can be re-tested during the screening window. Participants with reactive HIV tests will not be able to rescreen.*

*Note: Participants who practice receptive vaginal sex cannot be provided Descovy® as it is not approved for this indication.*

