## **8.6 Statistical Analysis**

This section briefly describes the final study analyses. Detailed technical specifications of the statistical analyses will be described in a separate Statistical Analysis Plan.

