### Sexually transmitted infections (STIs)

Descriptive summaries will be used to present the number of active bacterial STIs and the HBV infections at baseline as compared to selected subsequent visits for each study arm. Logistic regression models will be used to calculate STI prevalence at each time point and Poisson regression models will be used to calculate STI incidence by arm.

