### Baseline laboratory data

Descriptive statistics will be obtained to summarize all baseline variables. Logistic regression models will be used for estimating prevalence of baseline conditions.

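### On the protocol's own markers, entry criteria 8a and 8c fix the baseline prevalence of renal insufficiency and HBV infection at zero among enrolled participants, and no visible section plans a screened denominator

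*Combined protocol and SAP*

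**What the plan says.** Section 2.2 sets a secondary objective of collecting baseline laboratory data to judge the cohort's "suitability for future PrEP intervention studies (e.g., prevalence of renal insufficiency", followed by HBV and HCV infection and an open-ended etc. Section 8.2.2 repeats the examples, "prevalence of renal insufficiency, hepatitis B virus (HBV) infection, hepatitis C virus (HCV) infection", and gives the endpoint as "Baseline laboratory data on all participants". It defines neither condition and names no analysis set.

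Under Baseline laboratory data, Section 8.6.2 plans descriptive summaries and adds: "Logistic regression models will be used for estimating prevalence of baseline conditions". Under Sexually transmitted infections, the same section plans a summary of "HBV infections at baseline as compared to selected subsequent visits for each study arm".

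Section 4.1, criterion 8, requires clearance of at least 60 "mL/minute using the Cockcroft-Gault equation" (8a) and "HBV surface antigen (HBsAg) negative" (8c). A failing laboratory value other than a reactive HIV test may be repeated within the screening window.

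Appendix Ia schedules creatinine clearance and HBV testing at Screening and not at Enrollment. After that, HBV is tested only at Week 78. The creatinine-clearance note in Appendix II treats the Screening Visit as baseline.

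Section 8.6 defers detail: "Detailed technical specifications of the statistical analyses will be described in a separate Statistical Analysis Plan". That plan is not in the text reviewed.

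**The concern.** The objective asks how common certain conditions are. The entry criteria remove people with two of the conditions given as examples, using the same test result that then serves as the baseline value. A prevalence computed among those who pass is decided before any data are collected.

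If the report follows the natural reading of the plan, it may present 0% renal insufficiency and 0% HBV infection as findings about the cohort. Planners of later PrEP studies, whom this objective serves, could take those figures as evidence that few people would be excluded on these grounds. The results that answer their question belong to people who were screened and not enrolled, and no visible section plans to analyse them.

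**Working it through.** The documents state no prevalence, expected count or precision for this endpoint, so there is no figure of the plan's to reproduce. The check sets the sections side by side and then does some simple arithmetic.

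**Step 1: definitions.** The protocol defines neither condition, so the check uses the markers it uses elsewhere. The only clearance thresholds in the text are 60 mL/min (Section 4.1 and Appendix II) and 30 mL/min (Appendix II). For HBV, the entry criterion uses HBsAg, and the AST/ALT guidance in Appendix II names HBsAg before it speaks of confirmed hepatitis B.

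**Step 2: which value is baseline.** Neither test is repeated at Enrollment, so the baseline value is the qualifying value. Everyone enrolled has clearance of at least 60 and HBsAg negative on that value. The number below 60 (and so below 30) is 0, and the number HBsAg positive is 0. A person who failed first and passed on re-test has an earlier abnormal result, so the zero holds for the qualifying value only.

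**Step 3: the enrolled figures.** Planned enrollment is about 310, or 155 per arm at 1:1. With 0 events, the exact 95% upper limit is 1 − 0.025^(1/n):
- 0/310: 1 − 0.025^(1/310) = 1.18%
- 0/155: 1 − 0.025^(1/155) = 2.35%

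The zero is set by selection, so neither limit describes the rate in the people who came forward.

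**Step 4: the planned model.** An intercept-only logistic fit to 0/310 has log-likelihood −310 × ln(1 + e^b). This is −2.08 at b = −5, −0.014 at b = −10 and practically 0 at b = −20. It keeps rising as b falls, so there is no finite estimate.

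**Step 5: what an enrolled zero leaves open.** Section 8.4 expects 560 screened for 310 enrolled and calls this 80%. The two figures disagree: 310/560 = 55.4%, while 310/0.80 = 387.5, about 388 screened. On the qualifying value, every case lies among those not enrolled:
- 560 − 310 = 250, so a screened prevalence of up to 250/560 = 44.6% is logically possible
- 388 − 310 = 78, so up to 78/388 = 20.1%

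These ceilings would need every person not enrolled to have the condition. They show only that an enrolled zero says almost nothing about the screened population.

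**Step 6: what a screened denominator would give.** The documents give no rate, so the rates here are assumptions. If all 560 had a result:

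| Assumed rate | Count | Exact 95% CI |
|---|---|---|
| 1% | 6/560 | 0.4% to 2.3% |
| 2% | 11/560 | 1.0% to 3.5% |
| 5% | 28/560 | 3.3% to 7.1% |

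Fewer than the number screened will be tested (Section 6.2), so real intervals would be wider.

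**Step 7: the HBV comparison over time.** HBV is tested only at Screening and Week 78. On the HBsAg reading, the comparison with baseline in Section 8.6.2 is therefore the Week 78 count.

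**The case against.** **The conditions are examples, and undefined.** The list is open, and the endpoint is baseline laboratory data in general. HBsAb and HBcAb-total are also measured, and clearance of 60 and above still varies. A renal cut-off above 60, or HBV defined by core antibody, could give a non-zero prevalence. This stands. A reader might infer that the whole objective is empty, or that HCV prevalence is also forced to zero. The documents support neither: HCV antibody is not an entry criterion, although the Section 4.2 exclusion for liver disease may lower its prevalence.

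**The denominator may already include people screened.** Sections 4.1, 6.2 and 10.7 use the word participants for people who are not enrolled. The note in Table 3 speaks of TGW who screen positive for HBV, and Section 9.4 describes HBV and HCV testing of participants with referral. This lends some support to a screened reading, so the denominator is ambiguous. Against it, the objective refers to the cohort and the HBV summary is by study arm, both of which point to enrolled people. No visible section states a screened denominator.

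**The unseen SAP may settle it.** Analysis sets and definitions are ordinary SAP content, so the absence can be claimed only for the text available.

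**The model failure matters little.** Section 8.6.2 also plans descriptive statistics, so a zero count would be tabulated whether or not the model converges. This stands. It would overstate the case to say that the logistic plan makes the endpoint unreportable.

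**Screen failures may be outside the question.** If the aim is only whether these enrolled people suit later studies, they are another population. But then a prevalence of conditions that bar entry tells the reader nothing about those people that the criteria do not already say.

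**Conclusion.** The point holds in conditional form and is minor. If renal insufficiency means clearance below 60 mL/min and HBV infection means HBsAg positive, both baseline prevalences among enrolled participants are 0/310 on the qualifying value by design, and they cannot inform suitability for future PrEP studies. This rests on three assumptions: those two definitions, the enrolled reading of the denominator, and no contrary provision in the separate SAP.

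The 44.6% and 20.1% ceilings might be read as the size of a bias. They are logical bounds and estimate nothing. The HBV comparison with later visits is not an error either, because zero at entry followed by a Week 78 count does show new positives; it mainly needs a clearer label.

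Only part of one descriptive secondary objective is touched. The primary comparison and the power are not affected.

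**What to change.** In Section 8.2.2, define the two conditions for analysis, for example by the markers in criteria 8a and 8c, and state the denominator. Report their prevalence among all TGW screened with a result, enrolled plus screen failures. Count each person once under a stated rule for repeat tests and re-screening, both of which the protocol allows. Give the numbers screened, tested and not tested.

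In Section 8.6.2, give exact binomial 95% confidence intervals for these prevalences, and label any zero in the enrolled cohort as set by eligibility. Describe HBsAg positivity at Week 78 as new among participants negative at entry.

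Separately, reconcile Section 8.4: 310 of 560 is 55.4%, and an 80% yield would mean about 388 screened.

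The cost is wording plus data entry of screening results that sites already generate. No extra test, visit or participant is needed. Samples from people not enrolled may be discarded (Section 10.7), so the results would come from site laboratory reports, and sites must confirm that the screening consent covers this use. The downside is an incomplete denominator: screening stops once ineligibility is known (Section 6.2), so who gets tested depends on test order, and the estimate describes study volunteers who were screened and tested, not all TGW.
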